9. IMMUNOGENICITY

9.1. Primary Analysis

As described in the complete clinical protocol, secondary immunogenicity endpoints will be measured using a standard plaque reduction neutralization assay (PRNT₅₀). A PRNT₅₀ assay uses a set amount of virus and serial dilutions of serum. The reciprocal of the last serum dilution that demonstrates $\geq 50\%$ neutralization of the virus inoculum is defined as the PRNT₅₀ titer for that sample. The geometric mean PRNT₅₀ titer (GMT) and associated exact Blaker 95% confidence interval will be presented by treatment group at baseline Days 15 and 29 after the first vaccination and Days 15, 29, 57 and 180 after the second vaccination in both the FA ([Table 30](#)) and PP ([Table 31](#)) populations, as defined in [Section 6.4.2](#). For each study day, the number of subjects in the FA or PP population with available immunogenicity data at the particular study day will be presented and used in calculations. A listing of all PRNT₅₀ and viremia results will be provided ([Listing 14](#) and [Listing 15](#)). The reverse cumulative distribution of the PRNT₅₀ titer by Study Day and treatment group will also be generated for each vaccination in both FA and PP populations ([Figure 11](#), [Figure 12](#), and [Figure 13](#)).

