9.4.3 Analysis of Secondary and Exploratory Outcome Measures (Immunogenicity)

Basic descriptive statistics, such as point estimates and 95% confidence intervals, and graphical summaries, such as the reverse cumulative distribution, of seroconversion rates and geometric mean titer (GMT) will be computed by intervention at baseline, 15 and 29 days after the first vaccination, and 15, 29, 57, and 180 days after the second vaccination. YFV-specific neutralizing antibody titers may be measured through a standard plaque reduction neutralizing titer [PRNT₅₀] assay, or utilizing a Log₁₀ Neutralizing Index (LNI) assay [5, 38]. For the purposes of this study, and in line with recent yellow fever vaccine clinical trials [7, 8], antibody titers will be assessed using the PRNT₅₀ assay, and seroconversion will be defined as a PRNT₅₀ neutralizing antibody titer of $\geq 1:10$. The limit of detection in the neutralizing assay will be a titer of <10 . For the purposes of determining seroconversion rates and GMT, antibody titers of <10 will be assumed to be 5 (one dilution step below the assay limit value).

Rates of seroconversion will be summarized by tabulating the frequency of positive responses by treatment group at Day 29 after first vaccination and Day 57 after second vaccination. Response rates for each treatment group will be presented with their corresponding 95% confidence interval estimates at each time point. The relationship between the proportion of responders and dosage will be examined using logistic regression. The distribution of antibody titers will also be graphically summarized using the reverse cumulative frequency distribution of titers for each treatment group.

The PRNT₅₀ titers at days 15 and 29 after first vaccination and at days 15, 29, and 57 following second vaccination will be summarized graphically for each treatment group. The geometric mean titer (GMT) and pair-wise differences of each treatment group will also be presented with 95% confidence intervals. The relationship between GMT and dosage will be examined using standard linear regression methods. Secondary outcome measures include:

- Percentage of subjects achieving seroconversion ($\geq 1:10$ in plaque reduction neutralizing titer [PRNT₅₀] titer) at day 29 after first vaccination and at day 29 after second vaccination.

- Geometric mean neutralizing titers at days 15 and 29 after first vaccination and at days 15, 29, and 57 following second vaccination.

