3.2. Endpoints

Primary Outcome Measures:

- Occurrence of all serious adverse events (SAEs) at any time during the study
- Occurrence of all Grade 3 unsolicited adverse events (AEs) from first vaccination through Day 29 after the second vaccination
- Occurrence of all Grade 3 laboratory toxicities from first vaccination through Day 15 after the second vaccination
- Occurrence of solicited local AE and reactogenicity signs and symptoms in the 7 days after each vaccination
- Occurrence of solicited systemic AE and reactogenicity signs and symptoms in the 7 days after each vaccination
- Occurrence of any AE through Day 29 after the second vaccination

Secondary Outcome Measures:

- Percentage of subjects achieving seroconversion ($\geq 1:10$ in plaque reduction neutralizing titer [PRNT₅₀] titer, at Day 29 after first vaccination and at Day 29 after second vaccination
- Geometric mean neutralizing titers at days 15 and 29 after first vaccination and at Days 15, 29, and 57 following second vaccination
- Reverse cumulative distribution curve of neutralizing titers on Days 15 and 29 after first vaccination and at Days 15, 29 and 57 after the second vaccination for each dose group and for all dose groups combined

Exploratory Outcome Measures:

- Geometric mean neutralizing titers at Day 180 following second vaccination
- Reverse cumulative distribution curve of neutralizing titers on Day 180 after the second vaccination for each dose group and for all dose groups combined

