3.3. Study Definitions and Derived Variables

Seroconversion is defined as a PRNT₅₀ neutralizing antibody titer of $\geq 1:10$. The limit of detection in the neutralizing assay will be a titer of <10 . For the purposes of determining seroconversion rates and GMT, antibody titers of <10 will be assumed to be 5 (one dilution step below the assay limit value).

For exploratory analysis using the LNI measurement the limit of detection will be defined as 0.70, and seroconversion is defined as an LNI value ≥ 0.70 . For the purposes of determining seroconversion rates and GMT, LNI titers of <0.70 will be set to value of 0.35 (one-half the limit of detection).

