6.6. Missing Data

Missing safety and/or immunogenicity data will not be imputed. No search for outliers will be performed. However, the logarithmic transform will be used as appropriate to improve the distributional properties of the immunogenicity data and reduce the impact of potential outliers.

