9.2. Secondary and Exploratory Analysis

An alternative approach to assessing neutralizing titers is using a constant amount of serum and serial dilutions of the virus inoculum. This approach is referred to as a log-neutralizing index (LNI) and has been used in the past to assess immunogenicity following vaccination with YFV vaccine candidates. The log neutralizing index (LNI) and associated exact Blaker 95% confidence interval will be presented by treatment group at baseline Days 15 and 29 after the first vaccination and Days 15, 29, 57 and 180 after the second vaccination in both the FA ([Table 30](#)) and PP ([Table 31](#)) populations, as defined in [Section 6.4.2](#). A listing of all LNI results will be provided ([Listing 14](#)). For each study day, the number of subjects in the FA or PP population with available immunogenicity data at the particular study day will be presented and used in calculations. The reverse cumulative distribution of the LNI titer by Study Day and treatment group will also be generated for each vaccination in both the FA and PP populations ([Figure 15](#), [Figure 16](#), [Figure 17](#), and [Figure 18](#)).

The number of subjects seroconverting by either the LNI or PRNT₅₀ measurements will be enumerated in either the FA ([Table 32](#)) or PP ([Table 33](#)) populations.

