	Max Severity Post Baseline	HydroVax-002 YFV -1 mcg	XX	X	X.X	X	X.X	X	X.X	X	X.X
		HydroVax-002 YFV -5 mcg	XX	X	X.X	X	X.X	X	X.X	X	X.X
		Placebo	XX	X	X.X	X	X.X	X	X.X	X	X.X

Repeat for all laboratory parameters...

The "Max Post Baseline" rows indicate the maximum severity experienced by each subject at any time point post baseline, including unscheduled assessments.

N = Number of subjects in the Safety population with available laboratory results.

Implementation note: This table will be repeated for all hematology, blood chemistry and urinalysis parameters.

Table 29: Abnormal Laboratory Results Related to Study Treatment by Parameter, Maximum Severity, Study Day, Treatment Group and Parameter – Any Parameter

Parameter	Time Point	Treatment Group	Mild/ Grade 1			Moderate/ Grade 2		Severe/ Grade 3	
			N	n	%	n	%	n	%
[Parameter 1]	Day 4 Post-Dose 1	HydroVax-002 YFV -1 mcg	XX	x	x.x	x	x.x	x	x.x
		HydroVax-002 YFV -5 mcg	XX	x	x.x	x	x.x	x	x.x
		Placebo	XX	x	x.x	x	x.x	x	x.x
	Day 15 Post-Dose 1	HydroVax-002 YFV -1 mcg	XX	x	x.x	x	x.x	x	x.x
		HydroVax-002 YFV -5 mcg	XX	x	x.x	x	x.x	x	x.x
		Placebo	XX	x	x.x	x	x.x	x	x.x
	Day 29 Post-Dose 1	HydroVax-002 YFV -1 mcg	XX	x	x.x	x	x.x	x	x.x
		HydroVax-002 YFV -5 mcg	XX	x	x.x	x	x.x	x	x.x
		Placebo	XX	x	x.x	x	x.x	x	x.x
	Day 4 Post-Dose 2	HydroVax-002 YFV -1 mcg	XX	x	x.x	x	x.x	x	x.x
		HydroVax-002 YFV -5 mcg	XX	x	x.x	x	x.x	x	x.x
		Placebo	XX	x	x.x	x	x.x	x	x.x
	Day 15 Post-Dose 2	HydroVax-002 YFV -1 mcg	XX	x	x.x	x	x.x	x	x.x
		HydroVax-002 YFV -5 mcg	XX	x	x.x	x	x.x	x	x.x
		Placebo	XX	x	x.x	x	x.x	x	x.x
	Max Severity Post Baseline	HydroVax-002 YFV -1 mcg	XX	x	x.x	x	x.x	x	x.x
		HydroVax-002 YFV -5 mcg	XX	x	x.x	x	x.x	x	x.x
		Placebo	XX	x	x.x	x	x.x	x	x.x

Repeat for all laboratory parameters...

The “Max Post Baseline” rows indicate the maximum severity experienced by each subject at any time point post baseline, including unscheduled assessments.

N = Number of subjects in the Safety population with available laboratory results.

Implementation note: This table will be repeated for all hematology, blood chemistry and urinalysis parameters.

Table 30: PRNT₅₀ Geometric Mean Titer (GMT) and Log Neutralizing Titer Index (LNI) Results with 95% Confidence Intervals by Study Day and Treatment Group, Full Analysis Population

Visit	HydroVax-002 YFV 1 mcg			HydroVax-002 YFV 5 mcg			Placebo		
	N	GMT	95% CI	N	GMT	95% CI	N	GMT	95% CI
PRNT₅₀									
Day 1 (pre-vaccination)	XX	X.XX	X.XX, X.XX	XX	X.XX	X.XX, X.XX	XX	X.XX	X.XX, X.XX

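### SAP 9.1 and 9.2 name an exact Blaker interval, a method for counts, for the geometric mean PRNT50 titer and the LNI; it cannot fill the 95% CI columns of Tables 30 and 31

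*SAP*

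**What the plan says.** SAP 3.2 lists as a secondary outcome "Geometric mean neutralizing titers at days 15 and 29 after first vaccination and at Days 15, 29, and 57 following second vaccination". SAP 9.1 defines a PRNT50 titer as a reciprocal serum dilution for each sample and then attaches an interval to its geometric mean: "titer (GMT) and associated exact Blaker 95% confidence interval will be presented by treatment group at baseline", and at each later visit. SAP 9.2 does the same for the exploratory assay: "The log neutralizing index (LNI) and associated exact Blaker 95% confidence interval will be presented by treatment group".

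Both sections send the results to Tables 30 (full analysis population) and 31 (per protocol population). Table 30 is headed "Geometric Mean Titer (GMT) and Log Neutralizing Titer Index (LNI) Results with 95% Confidence Intervals by Study Day and Treatment Group, Full Analysis Population". Its columns are N, GMT and 95% CI for each group. There is no responder count, and no footnote names an interval method. The LNI rows sit under the same GMT column header.

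Three other places bear on the interval:

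- SAP 6.6 says "the logarithmic transform will be used as appropriate to improve the distributional properties of the immunogenicity data". It gives no interval formula.
- Protocol 9.4.3 says of the GMT that it and "pair-wise differences of each treatment group will also be presented with 95% confidence intervals". It names no method. It also names linear regression, but for the relation of GMT to dose.
- SAP 3.3 sets the floor values. A PRNT50 titer below 10 "will be assumed to be 5 (one dilution step below the assay limit value"), and an LNI below 0.70 becomes 0.35. The LNI rule opens "For the purposes of determining seroconversion rates and GMT, LNI titers of", so LNI is treated there as something that has a GMT.

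**The concern.** Blaker's method inverts a test on the parameter of a one-parameter discrete distribution, usually a binomial proportion. Its inputs are the count and the sample size. A GMT is the antilog of a mean of log titers, and its uncertainty depends on the spread of those logs, which Blaker never sees. The rule as written returns nothing that can be printed beside a GMT.

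The trial describes its purpose as estimation, and GMT is one of three secondary outcomes. Protocol 9.4.4.2 wants the SAP final before any unblinding, so that the analyses are defined in advance. For this interval they are not: whoever programs the tables must replace the stated rule with one of their own.

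**Working it through.** **The plan's own figure.** Neither document states a number for a GMT or LNI interval. The only exact limit given as a number is the 30.8% upper bound for 0 events in 10 (protocol 9.2.1, SAP 5). It reproduces as the two-sided Clopper-Pearson limit: 1 − 0.025^(1/10) = 0.3085. Blaker for 0/10 gives 28.3%. So the one exact figure in the plan is not a Blaker limit, which is a further reason to name the method wherever an exact interval is meant.

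**What Blaker uses.** For each p, let T(k) be the smaller of P(X ≤ k) and P(X ≥ k) under a binomial(n, p). The 95% interval is the set of p for which P(T(X) ≤ T(x)) exceeds 0.05. Only x and n enter.

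**Illustration.** The titers are made up; group size n = 10 is from SAP 5. The comparison is a t interval on log10 titers, GMT ×/÷ 10^(t·SD/√n), with t = 2.262 at 9 df.

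- Set A, five values of 5 and five of 10: GMT = √(5 × 10) = 7.07; log10 SD 0.159. Half-width 2.262 × 0.159/3.162 = 0.114, a factor of 1.30. Interval 5.4 to 9.2.
- Set B, five values of 5, then 10, 40, 160, 320, 640: GMT 23.0; log10 SD 0.849. Half-width 2.262 × 0.849/3.162 = 0.607, a factor of 4.05. Interval 5.7 to 93.0.
- Blaker: both sets are 5/10 at or above 10, so both give 22.2% to 77.8%, which is a proportion and not a titer.

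**How many cells.** Secondary GMT intervals: 5 visits × 3 groups = 15 in each of two overlapping populations. All cells in Tables 30 and 31: 7 visits × 3 groups × 2 assays × 2 populations = 84. The other 54 are LNI (42) or PRNT50 at baseline and Day 180 (12).

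**Width to expect from a t interval.** The documents give no titer SD. Assuming a log10 SD of 0.5 (range 0.3 to 0.7), the factor is 2.28 (1.64 to 3.17) at n = 10 and, with t = 2.776 at 4 df, 4.18 (2.36 to 7.40) at the placebo n = 5.

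**Behavior at the floor.** The replacement needs a rule here.

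- If all five placebo titers are set to 5, the t interval is 5 to 5, with zero width. If 1% to 10% of placebo samples read 10 or more (assumption), a placebo cell is entirely at the floor with probability 0.99^5 = 0.95 to 0.90^5 = 0.59.
- The remaining 5% to 41% of such cells mix floor and measured values, so a footnote limited to all-floor cells would miss them.
- In mixed cells the lower limit can fall below 5, although no GMT can. Nine 5s and one 40: GMT 6.2; log10 SD 0.286; factor 10^(2.262 × 0.286/3.162) = 1.60; interval 3.8 to 9.9.

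**LNI label.** LNI is already a log10 index. For made-up values 0.35, 0.35, 0.35, 0.7, 0.9, 1.1, 1.2, 1.4, 1.6, 1.8 the arithmetic mean is 9.75/10 = 0.975 (t interval 0.59 to 1.36). A geometric mean, which the column header would imply if taken literally, is 0.82.

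**The case against.** The strongest reply is that this is a misnamed method in a 25-subject descriptive study. SAP 6.7 plans no formal testing, and protocol 9.2.2 says the study is not powered for small to moderate immunogenicity differences. The log transform in SAP 6.6 and the linear regression in protocol 9.4.3 both point to normal theory on logs, so a log-scale t interval would very likely be used anyway. SAP 1 requires any deviation to be described and justified. All of this stands, and it keeps the consequence small. It does not supply the missing rule: neither passage states an interval, and the unusable method appears in two sections.

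One could also argue that titers on a dilution grid are discrete. They are, but the SAP offers no one-parameter discrete model whose parameter is the GMT, so Blaker still has nothing to invert.

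Some stronger readings are tempting and not supported:

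- A reader might infer that the eventual choice of method will change the reported GMT or LNI precision by a known amount. Nothing here shows that. The factors above vary an assumed SD under a single method and do not compare two usable ones.
- A reader might extend the point to the pair-wise GMT comparisons, where a Welch or pooled variance would matter. SAP 9.1 and 9.2 never assign Blaker to those comparisons.
- A reader might conclude that Blaker was meant for the cross-tabulated percentages of Tables 32 and 33. Those shells print 95% CI columns with no method named, and nothing in the text says so.

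**Conclusion.** The point holds and should be fixed. The interval rule stated for a secondary outcome (GMT) and an exploratory one (LNI) cannot be carried out, and nothing else in the documents replaces it. This conclusion rests on the text and on what Blaker's method takes as input. The titers, SDs and placebo positivity rates are assumptions used only for illustration.

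The effect of the Blaker wording is limited to precision statements: 15 secondary GMT intervals per population, plus the baseline, Day 180 and LNI cells. Point estimates, seroconversion percentages, sample size, halting and escalation are unaffected. The GMT label on LNI is a smaller matter of clarity: taken literally, it would call for a geometric mean of a log index. A reader might infer that the immunogenicity results would be invalid, or that all 84 cells are secondary-endpoint failures. Neither follows.

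**What to change.** - In SAP 9.1 and Tables 30 and 31, replace the Blaker wording with a t 95% interval (n − 1 df) on log10 PRNT50, back-transformed.
- In SAP 3.3, 9.2 and Tables 30 and 31, report LNI as an arithmetic mean with a t interval and drop the GMT label for it.
- Footnote every cell that contains substituted values (5 or 0.35) with the number at the floor. Where all values are at the floor, print below limit instead of a zero-width interval. Note that a lower limit under 5 (or 0.35) lies below the substituted value.
- Keep exact binomial intervals, such as Blaker, for seroconversion proportions.

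This costs SAP wording, table headers and footnotes, with no change to data or design. The pair-wise GMT comparisons and by-treatment-group seroconversion rates promised in protocol 9.4.3 have no shell in the SAP. That is a separate point, and it would need new outputs.

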9.2. Secondary and Exploratory Analysis

An alternative approach to assessing neutralizing titers is using a constant amount of serum and serial dilutions of the virus inoculum. This approach is referred to as a log-neutralizing index (LNI) and has been used in the past to assess immunogenicity following vaccination with YFV vaccine candidates. The log neutralizing index (LNI) and associated exact Blaker 95% confidence interval will be presented by treatment group at baseline Days 15 and 29 after the first vaccination and Days 15, 29, 57 and 180 after the second vaccination in both the FA ([Table 30](#)) and PP ([Table 31](#)) populations, as defined in [Section 6.4.2](#). A listing of all LNI results will be provided ([Listing 14](#)). For each study day, the number of subjects in the FA or PP population with available immunogenicity data at the particular study day will be presented and used in calculations. The reverse cumulative distribution of the LNI titer by Study Day and treatment group will also be generated for each vaccination in both the FA and PP populations ([Figure 15](#), [Figure 16](#), [Figure 17](#), and [Figure 18](#)).

The number of subjects seroconverting by either the LNI or PRNT₅₀ measurements will be enumerated in either the FA ([Table 32](#)) or PP ([Table 33](#)) populations.

10. SUMMARY OF CHANGES IN THE CONDUCT OF THE STUDY OR PLANNED ANALYSES

Version 6.0 of the protocol relegated the Day 180 immunogenicity objectives/outcomes to exploratory objectives/outcomes. In addition, the originally planned interim analysis was removed. Instead, an early analysis of the primary and secondary outcomes (and supporting summaries/analyses) was added to the protocol. Version 2.0 of the SAP incorporated these changes in addition to adding a viremia listing (Listing 15) that was erroneously excluded from Version 1.0 and fixing minor typos throughout the document.

11. ABBREVIATIONS

Abbreviation	Definition
AE	Adverse event
ALT	Alanine aminotransferase
AST	Aspartate aminotransferase
BMI	Body mass index
CI	Confidence interval
CRF	Case report form
DNA	Deoxyribonucleic acid
FA	Full analysis
GMT	Geometric mean titer
ID	Identification
LNI	Log neutralizing index
NIH	National Institutes of Health
NTI	Najit technologies, Inc.
PB	Preterm birth
PCR	Polymerase chain reaction
PFU	Plaque forming unit
PI	Principal investigator
PP	Per protocol
PRNT ₅₀	Plaque reducing neutralization test 50% reduction
PT	Preferred term
SAE	Serious adverse event
SDCC	Statistical data coordinating center
SMC	Safety monitoring committee
SOC	System organ class
TB	Term birth
USP	United States Pharmacopeia
WHO	World Health Organization
YFV	Yellow fever virus

13. LISTING OF TABLES, FIGURES, AND LISTINGS

Table, figure, and listing shells are presented.

APPENDIX 1. TABLE MOCK-UPS

Table 1: Ineligibility Summary of Screen Failures

Category	Reason/Criterion	N	%
Screened		x	-
Screened but not enrolled		x	100
Eligible but not enrolled	Any Reason	x	xx
	[reason 1]	x	xx
	[reason 2]	x	xx

Failing eligibility criteria	Any eligibility criterion ^a	x	xx
	Any inclusion criterion	x	xx
	[inclusion criterion 1]	x	xx
	[inclusion criterion 2]	x	xx

	Any exclusion criterion	x	xx
	[exclusion criterion 1]	x	xx
	[exclusion criterion 2]	x	xx

Denominator for percentages is the total number of subjects who were screened but not enrolled.

a: A subject could fail to meet more than one eligibility criterion. Thus, the sum of the counts of the individual reasons may add up to more than the total number of subjects who failed any eligibility criterion.

Table 2: Analysis Populations by Treatment Group

		HydroVax-002 YFV 1 meg (N=XX)		HydroVax-002 YFV 5 meg (N=XX)		Placebo (N=XX)		All Subjects (N=XX)	
Analysis Population	Reason Subjects Excluded	n	%	n	%	n	%	n	%
Safety Population	Included	x	x.x	x	x.x	x	x.x	x	x.x
	Excluded (Did not receive any vaccinations)	x	x.x	x	x.x	x	x.x	x	x.x
Post-Dose 1									
Full Analysis Population	Included	x	x.x	x	x.x	x	x.x	x	x.x
	Excluded	x	x.x	x	x.x	x	x.x	x	x.x
	Did not have pre- and post-baseline blood draws for YFV assay	x	x.x	x	x.x	x	x.x	x	x.x
	Did not receive any vaccinations	x	x.x	x	x.x	x	x.x	x	x.x
Per-Protocol Population	Included	x	x.x	x	x.x	x	x.x	x	x.x
	Excluded	x	x.x	x	x.x	x	x.x	x	x.x
	Did not receive any vaccinations	x	x.x	x	x.x	x	x.x	x	x.x
	Did not receive both vaccinations	x	x.x	x	x.x	x	x.x	x	x.x
	[Insert other reasons, e.g. protocol deviation]	x	x.x	x	x.x	x	x.x	x	x.x
Post-Dose 2									
Full Analysis Population	Included	x	x.x	x	x.x	x	x.x	x	x.x
	Excluded	x	x.x	x	x.x	x	x.x	x	x.x
	Did not have pre- and post-baseline blood draws for YFV assay	x	x.x	x	x.x	x	x.x	x	x.x
	Did not receive any vaccinations	x	x.x	x	x.x	x	x.x	x	x.x
Per-Protocol Population	Included	x	x.x	x	x.x	x	x.x	x	x.x
	Excluded	x	x.x	x	x.x	x	x.x	x	x.x
	Did not receive any vaccinations	x	x.x	x	x.x	x	x.x	x	x.x
	Did not receive both vaccinations	x	x.x	x	x.x	x	x.x	x	x.x
	[Insert other reasons, e.g. protocol deviation]	x	x.x	x	x.x	x	x.x	x	x.x

N = All enrolled subjects

Implementation Note: Above displays how dose-specific summaries will be presented if subject eligibilities differ by dose. Similar breakdowns by assay will be included if needed.

Table 3: Subject Disposition by Treatment Group

Subject Disposition	HydroVax-002 YFV 1 meg (N=XX)	HydroVax-002 YFV 5 meg (N=XX)	Placebo (N=XX)	All Subjects (N=XX)				
	n	%	n	%	n	%	n	%
Number of Subjects Screened	-	-	-	-	-	-	x	-
Number of Subjects Enrolled/Randomized	x	x.x	x	x.x	x	x.x	x	x.x
Number of Subjects Receiving First Vaccination	x	x.x	x	x.x	x	x.x	x	x.x
Number of Subjects Receiving Second Vaccination	x	x.x	x	x.x	x	x.x	x	x.x
Number of Subjects Terminating Early prior to Study Day 57 Post-Dose 2	x	x.x	x	x.x	x	x.x	x	x.x
Number of Subjects Terminating Early prior to Study Day 180 Post-Dose 2	x	x.x	x	x.x	x	x.x	x	x.x
Reasons for Early Discontinuation from the Study								
Enrolled But Treatment not Administered	x	x.x	x	x.x	x	x.x	x	x.x
Lost to Follow-up	x	x.x	x	x.x	x	x.x	x	x.x
Physician Decision	x	x.x	x	x.x	x	x.x	x	x.x
Withdrawal by Subject	x	x.x	x	x.x	x	x.x	x	x.x

Table 4: Distribution of Protocol Deviations by Category, Type, and Treatment Group

		HydroVax-002 YFV 1 mcg (N=xx)		HydroVax-002 YFV 5 mcg (N=xx)		Placebo (N=xx)		All Subjects (N=xx)	
Category	Deviation Type	# of Subj.	# of Dev.	# of Subj.	# of Dev.	# of Subj.	# of Dev.	# of Subj.	# of Dev.
Eligibility/enrollment	Any type	x	x	x	x	x	x	x	x
	<Deviation Type 1>	x	x	x	x	x	x	x	x
Follow-up visit schedule	Any type	x	x	x	xx	x	xx	xx	xx
	Missed visit/visit not conducted	x	x	x	x	x	x	x	x
	Out of window visit	x	x	x	x	x	x	xx	xx
Protocol procedure/assessment	Any type	x	x	x	x	x	x	x	x
	Required procedure done incorrectly	x	x	x	x	x	x	x	x
	Required procedure not conducted	x	x	x	x	x	x	x	x
	Specimen result not obtained	x	x	x	x	x	x	x	x
	Too few aliquots obtained	x	x	x	x	x	x	x	x
Treatment administration schedule	Any type	x	x	x	x	x	x	x	x
	Out of window visit	x	x	x	x	x	x	x	x
Blinding policy/procedure	Any type	x	x	x	x	x	x	x	x
	<Deviation Type 1>	x	x	x	x	x	x	x	x
Treatment administration	Any type	x	x	x	x	x	x	x	x
	<Deviation Type 1>	x	x	x	x	x	x	x	x

Table 5: Summary of Categorical Demographic and Baseline Characteristics by Treatment Group, All Enrolled Subjects

		HydroVax-002 YFV 1 mcg (N=XX)		HydroVax-002 YFV 5 mcg (N=XX)		Placebo (N=XX)		All Subjects (N=XX)	
Demographic Category	Characteristic	n	%	n	%	n	%	n	%
Gender	Female	x	x.x	x	x.x	x	x.x	x	x.x
	Male	x	x.x	x	x.x	x	x.x	x	x.x
Ethnicity	Hispanic or Latino	x	x.x	x	x.x	x	x.x	x	x.x
	Not Hispanic or Latino	x	x.x	x	x.x	x	x.x	x	x.x
	Not Reported	x	x.x	x	x.x	x	x.x	x	x.x
	Unknown	x	x.x	x	x.x	x	x.x	x	x.x
Race	American Indian or Alaskan Native	x	x.x	x	x.x	x	x.x	x	x.x
	Asian	x	x.x	x	x.x	x	x.x	x	x.x
	Native Hawaiian or other Pacific Islander	x	x.x	x	x.x	x	x.x	x	x.x
	Black or African American	x	x.x	x	x.x	x	x.x	x	x.x
	White	x	x.x	x	x.x	x	x.x	x	x.x
	Multi-Racial	x	x.x	x	x.x	x	x.x	x	x.x
	Unknown	x	x.x	x	x.x	x	x.x	x	x.x

Table 6: Summary of Continuous Demographic and Baseline Characteristics by Treatment Group, All Enrolled Subjects

Variable	Statistic	HydroVax-002 YFV 1 mcg (N=XX)	HydroVax-002 YFV 5 mcg (N=XX)	Placebo (N=XX)	All Subjects (N=XX)
Age (years)	Mean	X.X	X.X	X.X	X.X
	Standard Deviation	X.X	X.X	X.X	X.X
	Median	X.X	X.X	X.X	X.X
	Minimum	X	X	X	X
	Maximum	X	X	X	X
Height (cm)	Mean	XX.XX	XX.XX	XX.XX	XX.XX
	Standard Deviation	XX.XX	XX.XX	XX.XX	XX.XX
	Median	XX.XX	XX.XX	XX.XX	XX.XX
	Minimum	XX.X	XX.X	XX.X	XX.X
	Maximum	XX.X	XX.X	XX.X	XX.X
Weight (kg)	Mean	XX.XX	XX.XX	XX.XX	XX.XX
	Standard Deviation	XX.XX	XX.XX	XX.XX	XX.XX
	Median	XX.XX	XX.XX	XX.XX	XX.XX
	Minimum	XX.X	XX.X	XX.X	XX.X
	Maximum	XX.X	XX.X	XX.X	XX.X
BMI (kg/m ²)	Mean	XX.XX	XX.XX	XX.XX	XX.XX
	Standard Deviation	XX.XX	XX.XX	XX.XX	XX.XX
	Median	XX.XX	XX.XX	XX.XX	XX.XX
	Minimum	XX.X	XX.X	XX.X	XX.X
	Maximum	XX.X	XX.X	XX.X	XX.X

Table 7: Summary of Subjects with Pre-Existing Medical Conditions by MedDRA® System Organ Class and Treatment Arm

	HydroVax-002 YFV 1 meg (N=xx)	HydroVax-002 YFV 5 meg (N=xx)	Placebo (N=xx)		All Subjects (N=xx)	
MedDRA® System Organ Class	n	%	n	%	n	%
Any SOC	x	x.x	x	x.x	x	x.x
[SOC 1]	x	x.x	x	x.x	x	x.x
[SOC 2]	x	x.x	x	x.x	x	x.x
...	x	x.x	x	x.x	x	x.x

N=All enrolled subjects

n = Number of subjects reporting medical history within the specified SOC. A subject is only counted once per SOC.

Table 8: Summary of Concomitant Medications

		HydroVax-002 YFV 1 mcg (N=XX)		HydroVax-002 YFV 5 mcg (N=XX)		Placebo (N=XX)		All Subjects (N=XX)	
WHO Drug Code Level 1, Anatomic Group	WHO Drug Code Level 2, Therapeutic Group	n	%	n	%	n	%	n	%
Any Level 1 Codes	Any Level 2 Codes	x	x.x	x	x.x	x	x.x	x	x.x
Alimentary Tract And Metabolism	Any Level 2 Codes	x	x.x	x	x.x	x	x.x	x	x.x
	Antidiarrheals, Intestinal Anti-inflammatory/Antiinfective Agents	x	x.x	x	x.x	x	x.x	x	x.x
	Antiemetics And Antinauseants	x	x.x	x	x.x	x	x.x	x	x.x
	Drugs For Acid Related Disorders	x	x.x	x	x.x	x	x.x	x	x.x
	Drugs For Functional Gastrointestinal Disorders	x	x.x	x	x.x	x	x.x	x	x.x
	Mineral Supplements	x	x.x	x	x.x	x	x.x	x	x.x
	Vitamins	x	x.x	x	x.x	x	x.x	x	x.x
Anti-infective For Systemic Use	Any Level 2 Codes	x	x.x	x	x.x	x	x.x	x	x.x
	Antibacterials For Systemic Use	x	x.x	x	x.x	x	x.x	x	x.x
	Vaccines	x	x.x	x	x.x	x	x.x	x	x.x
Blood And Blood Forming Organs	Any Level 2 Codes	x	x.x	x	x.x	x	x.x	x	x.x
	Antianemic Preparations	x	x.x	x	x.x	x	x.x	x	x.x
	Antithrombotic Agents	x	x.x	x	x.x	x	x.x	x	x.x
Cardiovascular System	Any Level 2 Codes	x	x.x	x	x.x	x	x.x	x	x.x
	Diuretics	x	x.x	x	x.x	x	x.x	x	x.x
Dermatologicals	Any Level 2 Codes	x	x.x	x	x.x	x	x.x	x	x.x
	Antibiotics And Chemotherapeutics For Dermatological Use	x	x.x	x	x.x	x	x.x	x	x.x
	Antifungals For Dermatological Use	x	x.x	x	x.x	x	x.x	x	x.x
	Antipruritics, Incl. Antihistamines, Anesthetics, Etc.	x	x.x	x	x.x	x	x.x	x	x.x
	Corticosteroids, Dermatological Preparations	x	x.x	x	x.x	x	x.x	x	x.x
	Emollients And Protectives	x	x.x	x	x.x	x	x.x	x	x.x

		HydroVax-002 YFV 1 mcg (N=XX)		HydroVax-002 YFV 5 mcg (N=XX)		Placebo (N=XX)		All Subjects (N=XX)	
WHO Drug Code Level 1, Anatomic Group	WHO Drug Code Level 2, Therapeutic Group	n	%	n	%	n	%	n	%
	Other Dermatological Preparations	x	x.x	x	x.x	x	x.x	x	x.x
Genito Urinary System And Sex Hormones	Any Level 2 Codes	x	x.x	x	x.x	x	x.x	x	x.x
	Other Gynecologicals	x	x.x	x	x.x	x	x.x	x	x.x
	Sex Hormones And Modulators Of The Genital System	x	x.x	x	x.x	x	x.x	x	x.x
	Urologicals	x	x.x	x	x.x	x	x.x	x	x.x
Musculo-Skeletal System	Any Level 2 Codes	x	x.x	x	x.x	x	x.x	x	x.x
	Antiinflammatory And Antirheumatic Products	x	x.x	x	x.x	x	x.x	x	x.x
Nervous System	Any Level 2 Codes	x	x.x	x	x.x	x	x.x	x	x.x
	Analgesics	x	x.x	x	x.x	x	x.x	x	x.x
	Antiepileptics	x	x.x	x	x.x	x	x.x	x	x.x
	Psychoanaleptics	x	x.x	x	x.x	x	x.x	x	x.x
	Psycholeptics	x	x.x	x	x.x	x	x.x	x	x.x
Respiratory System	Any Level 2 Codes	x	x.x	x	x.x	x	x.x	x	x.x
	Antihistamines For Systemic Use	x	x.x	x	x.x	x	x.x	x	x.x
	Cough And Cold Preparations	x	x.x	x	x.x	x	x.x	x	x.x
	Drugs For Obstructive Airway Diseases	x	x.x	x	x.x	x	x.x	x	x.x
	Nasal Preparations	x	x.x	x	x.x	x	x.x	x	x.x
Sensory Organs	Any Level 2 Codes	x	x.x	x	x.x	x	x.x	x	x.x
	Ophthalmologicals	x	x.x	x	x.x	x	x.x	x	x.x
Various	Any Level 2 Codes	x	x.x	x	x.x	x	x.x	x	x.x
	General Nutrients	x	x.x	x	x.x	x	x.x	x	x.x
	Unspecified Herbal And Traditional Medicine	x	x.x	x	x.x	x	x.x	x	x.x

N = Number of subjects in the Safety population.

n = Number of subjects reporting taking at least one medication in the specific WHO Drug Class

Table 9: Summary of Adverse Events – Safety Population

Subjects ^a with	HydroVax-002 YFV		HydroVax-002 YFV		Placebo (N = xx)	
	1 mcg (N = xx)	%	5 mcg (N = xx)	%	n	%
At least one local solicited adverse event	x	x	x	x	x	x
At least one systemic solicited adverse event	x	x	x	x	x	x
At least one unsolicited adverse event	x	x	x	x	x	x
At least one related unsolicited adverse event	x	x	x	x	x	x
Mild (Grade 1)	x	x	x	x	x	x
Moderate (Grade 2)	x	x	x	x	x	x
Severe (Grade 3)	x	x	x	x	x	x
At least one severe (Grade 3) unsolicited adverse event	x	x	x	x	x	x
Related	x	x	x	x	x	x
Unrelated	x	x	x	x	x	x
At least one laboratory toxicity	x	x	x	x	x	x
At least one related laboratory toxicity	x	x	x	x	x	x
Mild (Grade 1)	x	x	x	x	x	x
Moderate (Grade 2)	x	x	x	x	x	x
Severe (Grade 3)	x	x	x	x	x	x
At least one severe (Grade 3) laboratory toxicity	x	x	x	x	x	x
Related	x	x	x	x	x	x
Unrelated	x	x	x	x	x	x
At least one serious adverse event ^b	x	x	x	x	x	x
At least one related, serious adverse event	x	x	x	x	x	x
At least one adverse event leading to early termination ^c	x	x	x	x	x	x

N = Number of subjects in the Safety Population and is the denominator for percentages

a: Subjects are counted once for each main category (i.e., non-indented row) regardless of the number of events. Subjects may be counted in more than one main category.

b: A listing of Serious Adverse Events is included in the Serious Adverse Event Listing.

c: As reported on the Adverse Event eCRF.

Table 10: Subject-Level Summary of Solicited Events by Symptom, Severity, Dose, and Treatment Group – Safety Population

Symptom	Severity	Post-Dose 1						Post-Dose 2						Post-Either Dose															
		HydroVax-002 YFV 1 mcg (N = xx)			HydroVax-002 YFV 5 mcg (N = xx)			Placebo (N = xx)			HydroVax-002 YFV 1 mcg (N = xx)			HydroVax-002 YFV 5 mcg (N = xx)			Placebo (N = xx)			HydroVax-002 YFV 1 mcg (N = xx)			HydroVax-002 YFV 5 mcg (N = xx)			Placebo (N = xx)			
		n	%	95% CI	n	%	95% CI	n	%	95% CI	n	%	95% CI	n	%	95% CI	n	%	95% CI	n	%	95% CI	n	%	95% CI	n	%	95% CI	
Any Symptom																													
Any Symptom	None	x	xx	x.x, x.x	x	xx	x.x, x.x	x	xx	x.x, x.x	x	xx	x.x, x.x	x	xx	x.x, x.x	x	xx	x.x, x.x	x	xx	x.x, x.x	x	xx	x.x, x.x	x	xx	x.x, x.x	
	Any Severity																												
	Mild																												
	Moderate																												
	Severe																												
Any Systemic Symptom																													
[Systemic Symptom 1]	None																												
	Any Severity																												
	Mild																												
	Moderate																												
	Severe																												
[Systemic Symptom 2]	None																												
	Any Severity																												
	Mild																												
	Moderate																												
	Severe																												

Symptom	Severity	Post-Dose 1						Post-Dose 2						Post-Either Dose														
		HydroVax-002 YFV 1 mcg (N = xx)			HydroVax-002 YFV 5 mcg (N = xx)			Placebo (N = xx)			HydroVax-002 YFV 1 mcg (N = xx)			HydroVax-002 YFV 5 mcg (N = xx)			Placebo (N = xx)			HydroVax-002 YFV 1 mcg (N = xx)			HydroVax-002 YFV 5 mcg (N = xx)			Placebo (N = xx)		
		n	%	95% CI	n	%	95% CI	n	%	95% CI	n	%	95% CI	n	%	95% CI	n	%	95% CI	n	%	95% CI	n	%	95% CI	n	%	95% CI
Any Local Symptom																												
[Local Symptom 1]	None																											
	Any Severity																											
	Mild																											
	Moderate																											
	Severe																											
[Local Symptom 2]	None																											
	Any Severity																											
	Mild																											
	Moderate																											
	Severe																											

N = Number of subjects in the Safety Population with solicited event data available for the specified time period and is the denominators for percentages.

The Any Symptom counts classify each subject by the maximum severity reported for the category; each subject is only counted once.

Table 11: Number and Percentage of Subjects Experiencing Systemic Solicited Events by Symptom, Severity, Day Post Dosing, and Treatment Group – Post-Dose 1 – HydroVax-002 YFV, 1 mcg

HydroVax-002 YFV - 1 mcg, N=XX													
		Post-Vac		Day 1		Day 2		Day 3		Day 4		Day 5-7	
Symptom	Severity	n	%	n	%	n	%	n	%	n	%	n	%
Any Systemic Symptoms	None	x	x.x	x	x.x	x	x.x	x	x.x	x	x.x	x	x.x
	Mild	x	x.x	x	x.x	x	x.x	x	x.x	x	x.x	x	x.x
	Moderate	x	x.x	x	x.x	x	x.x	x	x.x	x	x.x	x	x.x
	Severe	x	x.x	x	x.x	x	x.x	x	x.x	x	x.x	x	x.x
	Not Reported	x	x.x	x	x.x	x	x.x	x	x.x	x	x.x	x	x.x
Elevated Oral Temperature	None	x	x.x	x	x.x	x	x.x	x	x.x	x	x.x	x	x.x
	Mild	x	x.x	x	x.x	x	x.x	x	x.x	x	x.x	x	x.x
	Moderate	x	x.x	x	x.x	x	x.x	x	x.x	x	x.x	x	x.x
	Severe	x	x.x	x	x.x	x	x.x	x	x.x	x	x.x	x	x.x
	Not Reported	x	x.x	x	x.x	x	x.x	x	x.x	x	x.x	x	x.x
Feverishness	None	x	x.x	x	x.x	x	x.x	x	x.x	x	x.x	x	x.x
	Mild	x	x.x	x	x.x	x	x.x	x	x.x	x	x.x	x	x.x
	Moderate	x	x.x	x	x.x	x	x.x	x	x.x	x	x.x	x	x.x
	Severe	x	x.x	x	x.x	x	x.x	x	x.x	x	x.x	x	x.x
	Not Reported	x	x.x	x	x.x	x	x.x	x	x.x	x	x.x	x	x.x
Fatigue	None	x	x.x	x	x.x	x	x.x	x	x.x	x	x.x	x	x.x
	Mild	x	x.x	x	x.x	x	x.x	x	x.x	x	x.x	x	x.x
	Moderate	x	x.x	x	x.x	x	x.x	x	x.x	x	x.x	x	x.x
	Severe	x	x.x	x	x.x	x	x.x	x	x.x	x	x.x	x	x.x
	Not Reported	x	x.x	x	x.x	x	x.x	x	x.x	x	x.x	x	x.x

HydroVax-002 YFV - 1 mcg, N=XX													
		Post-Vac		Day 1		Day 2		Day 3		Day 4		Day 5-7	
Symptom	Severity	n	%	n	%	n	%	n	%	n	%	n	%
Headache	None	X	X.X	X	X.X	X	X.X	X	X.X	X	X.X	X	X.X
	Mild	X	X.X	X	X.X	X	X.X	X	X.X	X	X.X	X	X.X
	Moderate	X	X.X	X	X.X	X	X.X	X	X.X	X	X.X	X	X.X
	Severe	X	X.X	X	X.X	X	X.X	X	X.X	X	X.X	X	X.X
	Not Reported	X	X.X	X	X.X	X	X.X	X	X.X	X	X.X	X	X.X
Chills	None	X	X.X	X	X.X	X	X.X	X	X.X	X	X.X	X	X.X
	Mild	X	X.X	X	X.X	X	X.X	X	X.X	X	X.X	X	X.X
	Moderate	X	X.X	X	X.X	X	X.X	X	X.X	X	X.X	X	X.X
	Severe	X	X.X	X	X.X	X	X.X	X	X.X	X	X.X	X	X.X
	Not Reported	X	X.X	X	X.X	X	X.X	X	X.X	X	X.X	X	X.X
Nausea	None	X	X.X	X	X.X	X	X.X	X	X.X	X	X.X	X	X.X
	Mild	X	X.X	X	X.X	X	X.X	X	X.X	X	X.X	X	X.X
	Moderate	X	X.X	X	X.X	X	X.X	X	X.X	X	X.X	X	X.X
	Severe	X	X.X	X	X.X	X	X.X	X	X.X	X	X.X	X	X.X
	Not Reported	X	X.X	X	X.X	X	X.X	X	X.X	X	X.X	X	X.X
New muscle pain	None	X	X.X	X	X.X	X	X.X	X	X.X	X	X.X	X	X.X
	Mild	X	X.X	X	X.X	X	X.X	X	X.X	X	X.X	X	X.X
	Moderate	X	X.X	X	X.X	X	X.X	X	X.X	X	X.X	X	X.X
	Severe	X	X.X	X	X.X	X	X.X	X	X.X	X	X.X	X	X.X
	Not Reported	X	X.X	X	X.X	X	X.X	X	X.X	X	X.X	X	X.X

HydroVax-002 YFV - 1 mcg, N=XX													
		Post-Vac		Day 1		Day 2		Day 3		Day 4		Day 5-7	
Symptom	Severity	n	%	n	%	n	%	n	%	n	%	n	%
Aggravated muscle pain	None	X	X.X	X	X.X	X	X.X	X	X.X	X	X.X	X	X.X
	Mild	X	X.X	X	X.X	X	X.X	X	X.X	X	X.X	X	X.X
	Moderate	X	X.X	X	X.X	X	X.X	X	X.X	X	X.X	X	X.X
	Severe	X	X.X	X	X.X	X	X.X	X	X.X	X	X.X	X	X.X
	Not Reported	X	X.X	X	X.X	X	X.X	X	X.X	X	X.X	X	X.X
New joint pain	None	X	X.X	X	X.X	X	X.X	X	X.X	X	X.X	X	X.X
	Mild	X	X.X	X	X.X	X	X.X	X	X.X	X	X.X	X	X.X
	Moderate	X	X.X	X	X.X	X	X.X	X	X.X	X	X.X	X	X.X
	Severe	X	X.X	X	X.X	X	X.X	X	X.X	X	X.X	X	X.X
	Not Reported	X	X.X	X	X.X	X	X.X	X	X.X	X	X.X	X	X.X
Aggravated joint pain	None	X	X.X	X	X.X	X	X.X	X	X.X	X	X.X	X	X.X
	Mild	X	X.X	X	X.X	X	X.X	X	X.X	X	X.X	X	X.X
	Moderate	X	X.X	X	X.X	X	X.X	X	X.X	X	X.X	X	X.X
	Severe	X	X.X	X	X.X	X	X.X	X	X.X	X	X.X	X	X.X
	Not Reported	X	X.X	X	X.X	X	X.X	X	X.X	X	X.X	X	X.X

Table 12: Number and Percentage of Subjects Experiencing Systemic Solicited Events by Symptom, Severity, Day Post Dosing, and Treatment Group – Post-Dose 1 – HydroVax-002 YFV, 5 mcg

HydroVax-002 YFV - 5 mcg, N=XX													
		Post-Vac		Day 1		Day 2		Day 3		Day 4		Day 5-7	
Symptom	Severity	n	%	n	%	n	%	n	%	n	%	n	%
Any Systemic Symptoms	None	x	x.x	x	x.x	x	x.x	x	x.x	x	x.x	x	x.x
	Mild	x	x.x	x	x.x	x	x.x	x	x.x	x	x.x	x	x.x
	Moderate	x	x.x	x	x.x	x	x.x	x	x.x	x	x.x	x	x.x
	Severe	x	x.x	x	x.x	x	x.x	x	x.x	x	x.x	x	x.x
	Not Reported	x	x.x	x	x.x	x	x.x	x	x.x	x	x.x	x	x.x
